5.0 Study Procedures

5.1 Study Design

Research Design: A multi-center, repeat-measures randomized controlled mixed-methods trial.

Study Population: The proposed study will focus on Internal Medicine physicians who are part of inpatient care teams and nurses providing care on medical and medical/surgical units at LTC Charles S. Kettles VAMC in Ann Arbor, MI and MEDVAMC in Houston, TX. Medical students, surgical physicians, and physicians on sub-specialty teams will not be included. At both participating facilities the inpatient care teams are predominately composed of 1 attending, 1 senior resident, 2 interns, and up to 3 medical or physician assistant students. Interns and senior residents are usually assigned to a team for 4-week blocks (occasionally 2 weeks), while attendings rotate approximately every 2 weeks. The Ann Arbor VAMC has 3 medical or medical/surgical inpatient units, while MEDVAMC has 5 units. At both facilities each nursing unit employs between 20-30 nurses. We will aim to recruit approximately 30 attendings, 72 residents and 40 nurses at Ann Arbor VAMC. As MEDVAMC is larger, with a greater number of inpatient care teams and nursing units than the Ann Arbor VAMC, we will aim to recruit approximately 40 attendings, 72 residents and 90 nurses. Our target study sample size is a total of 344 physicians and nurses (167 intervention/177 control). For Aim 3, we plan to interview approximately 8 physician team members and 4-6 nurses from the intervention arm at each site.

General Study Overview and Outcome Measures:

A summary of the proposed study activities at each participating site is presented in **Table 2** below.

Table 2: Overview of Study Activities at Each Study Site

| Study Detail | Physicians | Nurses |
|----------------------------------|--|--|
| Target | Attendings, senior residents and interns on inpatient medicine teams | Nurses on medical or medical/surgical units |
| Teams/Units Participating | 2 teams each month for 12 months randomized to intervention or control arm at each site | 2 units (1 intervention; 1 control) at Ann Arbor VAMC & 4 units (2 intervention; 2 control) at MEDVAMC randomized once & followed for 12-months |
| Estimated number of participants | 107 intervention and 107 control | 20 intervention and 20 control at Ann Arbor VAMC; 40 intervention and 50 control at MEDVAMC |
| Habituation Period | 1 month | 1 month |

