Randomization – At each study site the participating physician teams and nursing units will be randomly assigned into one of two study arms (intervention/control). For physician teams, this will occur on a rolling basis for 12 months with 2 physician teams randomly selected at each site each month for participation (1 intervention, 1 control). Once randomized, an email will be sent to the initial attending of the team introducing the study and asking them to reply to the email if they would prefer to opt out and not have their team participate in the randomized controlled trial. If the attending physician from a team refuses to allow their team to participate, the next team identified from the randomized list will be approached to participate. If a new attending joins the team mid-month, they will be approached to participate in the study, but will be automatically assigned to the same randomization group as the rest of their team.

Similarly, a total of 2 medical/surgical units from VAAHS (1 intervention, 1 control) and 4 medical/surgical units from MEDVAMC (2 intervention, 2 control) will be randomly selected to participate in the nurse portion of the project. The nurse manager for each

selected unit will then be approached to obtain approval for the unit to participate. If a nurse manager declines, the next unit on the list will be selected.

For both physicians and nurses, an independent statistician will allocate the teams and units in a concealed fashion, using a computer-generated randomization schema. The physicians and nurses from the intervention groups will receive both independent and group-facilitated mindfulness education, will be encouraged to use a mindfulness mobile app as a practice reminder and additional resource, and instructed to integrate moments of mindfulness with repeated episodes of hand hygiene during the course of caring for patients. The control groups will receive no such education or intervention and will continue as usual.

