Group-Facilitated Components - At each site, the site lead/mindfulness champion will lead guided discussions with participants that will focus on how principles of mindfulness can be used to influence a clinician’s state of mental presence, allowing for moments of clarity, insight, and reflection, and potentially enhanced provider and patient safety. Group discussions will address how principles of mindfulness can be

implemented to generate reflective pauses during moments of hand hygiene while providing clinical care. Discussion leads may share personal anecdotes and clinical examples of instances where stopping to be aware of physical and emotional state influenced decision-making, patient care, and personal feelings. As the group-facilitated discussions are also intended to foster a sense of interpersonal support, participants will be encouraged to participate in the discussion, provide insights on learning and practicing mindfulness, share experiences, and ask questions on integrating mindfulness into clinical and hand hygiene practices. Discussions will also address questions and feedback on the self-directed components discussed above. For physician participants, group-facilitated discussions lasting approximately 15 minutes will be offered every other week throughout the intervention phase at each site. For nurse participants, group-facilitated discussions lasting up to 30 minutes will be offered every week throughout the intervention phase at each site. Given the circumstances brought on by the COVID-19 pandemic and to offer greater flexibility, these discussions will be conducted either in person or virtually through a VA approved online conferencing program such as Microsoft Teams or Zoom to promote participation and implementation fidelity across sites. These discussions will be audio recorded and transcribed as described in the qualitative data and analysis section below. Attendance at these meetings will be tracked as a measure of intervention engagement. Meeting logistics for the discussions will be addressed at each site accordingly and participants will be encouraged to attend as many discussions as possible.

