 - Nurses on intervention units will be sent an introductory email (**Appendix J**) with information about the study and asking to set up a time and place to discuss the study in more detail. If we are unable to reach the nurses through email, study staff will approach the nurses during their work shift and ask to set up a time to meet to discuss the study in private. Recruitment will occur in a private room or office using the attached recruitment script (**Appendix K**).
- Physicians: We estimate enrolling approximately 35 attending physicians, 24 senior residents, and 48 intern physicians into each arm of the study, which will result in a total of 214 physicians in total. All physicians from physician teams will be asked to participate in the randomized controlled trial and provide a signed informed consent. Each month one team at the Ann Arbor VAMC and 2 teams at MEDVAMC will be randomized to intervention and an equal number at each site will be randomized to control. A flyer describing the study (**Appendix S**) will be emailed (**Appendix T**) to teaching attendings to introduce the study. Before the beginning of the month, the initial attending physician on each selected team will be sent an email describing the study and giving them the option to opt out of their team being approached to participate (**Appendix L**). A time and place will be scheduled to discuss the study in more detail and obtain informed consent from the attending (**Appendix M**). Unless the attending indicates they do not want their team participating, the rest of the team will be sent an email describing the study (**Appendix L**). Then study staff will approach the senior resident and interns in the team rooms and ask to speak with them about the study (**Appendix M**). If there are others in the team room, the study staff will ask the residents to follow them to a private room to discuss the study in greater detail. If they are willing to participate, they will be asked to sign an informed consent document. The primary participants are the attending physicians on each team. If the initial attending declines allowing their team to participate, another team will be randomly selected and approached for participation. If any physicians choose to not participate, they will not be asked to participate in the intervention activities (if randomized to the intervention) or to complete the study surveys (both study

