5.6 Data Analysis

Quantitative Statistical Analysis (Aims 1 and 2): Differences in hand hygiene adherence and duration between intervention and control groups will be assessed using Fisher's exact test and t-test, as appropriate. Risk differences in adherence to duration of hand hygiene will be calculated for both intervention and control groups. Because the primary outcomes for Aim 1 (i.e., hand hygiene adherence and duration) are expected to occur frequently, we will use generalized linear models to evaluate differences in hand hygiene adherence and duration for the intervention versus control group, with the Poisson distribution (log link) and robust error variance. Models will account for provider type and level, and will incorporate clustering by physician team (and separately for nursing unit). Statistical significance will be calculated for the intervention (intervention vs. control) coefficient.

As a secondary outcome for Aim 1, we will assess changes and differences in hand hygiene perception based on response to select questions from PSHW. For Aim 2, mindfulness will be based on responses to FFMQ and well-being will be based on responses to WBI. FFMQ and WBI scales will be scored according to the published algorithms. Descriptive statistics will be used to summarize participant scores from pre- and post-intervention, as well as 6-month post-intervention follow-up assessments. Within-group paired-samples t-tests will be used to test for improvement in participant scores across the baseline, post-intervention (~14 days for physicians and 1-month for nurses), and 6-month post-intervention follow-up periods, for the intervention and control groups separately. Analyses will use list-wise deletion for missing data. Participants not completing all surveys will still be included in any analysis for which they provide data. For all analyses, p values less than 0.05 will be considered significant and all tests will be two-tailed. Analysis of covariance (ANCOVA) models will then be used to assess relative changes in mindfulness, well-being, and hand hygiene perceptions across groups, the most direct test of discriminant validity. In these models, post-test scores will be predicted by group status controlling for pre-test scores.

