Mindful Hand Hygiene to
Reduce Infections Among
Veterans While Enhancing
Provider Well-Being

NCT05261282

December 5, 2025

Data Analysis Plan

Differences in hand hygiene adherence and duration between intervention and control groups will be assessed using Fisher's exact test and t-test, as appropriate. Differences in adherence to duration of hand hygiene will be calculated for both intervention and control groups. As a secondary outcome for Aim 1, the investigators will assess changes and differences in hand hygiene perception based on responses to select questions from the PSHW. For Aim 2, mindfulness will be based on responses to the FFMQ and well-being will be based on responses to the WBI. Survey scales will be scored according to the published algorithms. Descriptive statistics will be used to summarize participant scores from baseline and post-intervention, as well as 6-month post-intervention (sustainability) follow-up assessments. Within-group paired-samples t-tests will be used to test for improvement in participant scores across the baseline, post-intervention (~14 days for physicians and 1-month for nurses), and 6-month post-intervention (sustainability) follow-up periods, for the intervention and control groups separately. Participants not completing all surveys will still be included in any analysis for which they provide data. Listwise deletion for observations containing less than 85% complete responses for the FFMQ or WBI items will be used. Missing values for observations with at least 85% responses for the FFMQ or WBI items will be imputed using the average value obtained from non-missing values within each respective subscale. Multilevel linear mixed regression models will be used to assess changes in mindfulness and well-being across groups and the effectiveness of the intervention. Mixed models account for correlation between repeat measurements on the same participant and accommodate missing data across time points. Random effects will be modeled to account for clustering of survey responses at the clinician level. All models will be adjusted for fixed effects for clinician role (physician/nurse) and intervention fidelity. For all analyses, p-values less than 0.05 will be considered significant and all tests will be two-tailed.

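### The SAP's FFMQ and WBI models leave out the randomised team or nursing unit, so the between-arm test is too liberal if change or post-intervention scores correlate within cluster

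*SAP*

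**What the plan says.** Protocol section 5.1 (Randomization) makes the group the unit of allocation: "At each study site the participating physician teams and nursing units will be randomly assigned into one of two study arms (intervention/control"). For nurses, Table 2 gives "2 units (1 intervention; 1 control) at Ann Arbor VAMC & 4 units (2 intervention; 2 control) at MEDVAMC randomized once", which is three units per arm.

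For the survey outcomes the SAP states: "Multilevel linear mixed regression models will be used to assess changes in mindfulness and well-being across groups and the effectiveness of the intervention". It then specifies the dependence structure: "Random effects will be modeled to account for clustering of survey responses at the clinician level". The fixed effects listed are clinician role and intervention fidelity. No term represents team, unit or site.

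Protocol section 5.6 treats the two aims differently. For hand hygiene adherence and duration: "Models will account for provider type and level, and will incorporate clustering by physician team (and separately for nursing unit"). For FFMQ, WBI and hand hygiene perceptions it uses ANCOVA: "In these models, post-test scores will be predicted by group status controlling for pre-test scores", with no cluster term. The power paragraph applies an ICC of 0.4 to adherence and mentions no clustering for FFMQ or WBI.

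**The concern.** A clinician random effect models the correlation between one person's repeat surveys. It does not model the correlation between different people who were allocated together. The SAP's word multilevel does not fill the gap, because the only level it names is the clinician.

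Whether the omission harms the standard error depends on the contrast and on the kind of clustering:

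- A team or unit effect that is constant over time cancels in an arm-by-time contrast, cancels only partly in ANCOVA, and does not cancel in a comparison of post-intervention levels.
- Clustering in change cancels in none of these.

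Correlated change is plausible by design. Part of the intervention is delivered in groups (protocol section 5.1: "As the group-facilitated discussions are also intended to foster a sense of interpersonal support"), and members of a team or unit share a rotation or a ward during follow-up. The SAP does not write down which term is tested.

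Aim 2's effectiveness claim rests on this arm effect. If scores cluster, its p-values are too small and its intervals too narrow. The 130 nurses come from only six randomised units, so they contribute most of the problem even though no nurse-only test is planned.

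**Working it through.** **Inputs from the documents.** Target 344 people, 167 intervention and 177 control (section 5.1). Physicians per arm: 35 + 24 + 48 = 107 (section 5.2). Teams per arm: 1 per site per month × 2 sites × 12 months = 24 (section 5.1, Randomization). Section 5.2 instead says "Each month one team at the Ann Arbor VAMC and 2 teams at MEDVAMC will be randomized to intervention", which gives 3 × 12 = 36. Nurses: 20 and 20 at Ann Arbor, 40 and 50 at MEDVAMC. Alpha is 0.05, two-sided.

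**Assumptions.** Units of 20/20/20 (intervention) and 20/25/25 (control); survey-score ICC from 0.01 to 0.10; two complete waves; within-person correlation 0.6.

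**The plan's own figure.** Section 5.6 claims more than 95% power for effect sizes of 0.3 to 0.75. For an unclustered two-sample test at 0.3 with N = 334: 0.3/√(1/167 + 1/167) = 2.741, and Φ(2.741 − 1.96) = 78.3%; N = 344 gives 79.4%. ANCOVA reaches 95% only with a baseline correlation near 0.65; a within-arm paired test with n = 167 gives 97.1%. The test behind the claim is not stated, so I do not call it wrong, but none of the versions that reach it includes clustering.

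**Design effect.** Per arm, DE = 1 + (Σm²/N − 1) × ICC, where m is cluster size. Splitting 107 physicians into 11 teams of 5 and 13 of 4 gives Σm² = 483.

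- Intervention: 483 + 1,200 = 1,683; 1,683/167 = 10.08; DE at ICC 0.05 = 1.454.
- Control: 483 + 1,650 = 2,133; 2,133/177 = 12.05; DE at ICC 0.05 = 1.553.
- Combined, weighted by 1/N: (1.454/167 + 1.553/177)/(1/167 + 1/177) = 1.50. So 344 people carry the information of about 344/1.50 = 229.
- By role at ICC 0.05: nurses 2.03, physicians about 1.17.

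**True error rate of the unclustered test**, 2 × (1 − Φ(1.96/√DE)):

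| ICC of change | DE | True two-sided error |
|---|---|---|
| 0.01 | 1.10 | 6.2% |
| 0.02 | 1.20 | 7.4% |
| 0.05 | 1.50 | 11.0% |
| 0.10 | 2.00 | 16.6% |

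With 36 teams per arm, DE at 0.05 is 1.45 and the error 10.4%, so the conflicting team counts do not change the conclusion.

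**Simulation by contrast** (null true, role-adjusted, 8,000 runs per cell), at ICC 0.01/0.02/0.05/0.10:

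| Type of clustering | Change contrast | ANCOVA | Post-score level |
|---|---|---|---|
| In change | 6/8/11/17% | 6/8/13/18% | not tabulated |
| Constant over time | about 5% throughout | 5/6/6/8% | 6/7/11/17% |

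**Where the cluster term must sit.** For arm-by-time at change ICC 0.05, with total change variance 2 × (1 − 0.6) = 0.8, the clinician-only model reports SE ≈ √(0.8 × (1/167 + 1/177)), which is 0.0966 after role adjustment. The true SD of that estimate is 0.1182 (ratio 1.22 = √1.50). Adding a cluster random intercept alone leaves the model SE at 0.0966. Adding a cluster-by-time effect gives 0.1141, which equals its true SD.

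**The case against.** The omission itself is not in dispute; the case against concerns its size and priority.

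- **One-arm clustering.** Group discussion, the only documented cause of correlated change, occurs in the intervention arm alone. Setting the control-arm DE to 1 gives a combined DE of 1.23 at ICC 0.05 and errors of about 5.5%, 6.1%, 7.8% and 10.6% across the four ICCs. This stands: under that mechanism the excess is roughly halved. It remains above 5%, and shared ward or rotation conditions could produce clustering in both arms.
- **Natural reading.** The SAP speaks of assessing changes, so an arm-by-time test is the likely intention, and time-constant clustering is then harmless. That is fair, and it makes the post-score figures secondary. The tested term is still not written, and clustering in change is not removed.
- **Non-response.** The figures assume full recruitment and complete surveys. At an assumed 80% or 60% response, the ICC 0.05 figure falls from 11.0% to 9.6% or 8.3% (7.1% or 6.5% with clustering in the intervention arm only). The 6-month wave was not simulated.
- **Untested parts of the remedy.** The cluster-by-time model was checked only with known variances, and crossed effects for attendings were not tested. Estimating a cluster-by-time variance from six nursing units may be unstable, which favours the simpler baseline-adjusted model.
- **Priority.** The protocol applies the term primary outcomes to adherence and duration, not to these scales. True, but Aim 2 is one of the three stated aims and this is its effectiveness test.

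**Conclusion.** The concern holds. Neither document puts the randomised cluster into the FFMQ and WBI comparison, although the protocol does so for the hand hygiene outcomes of the same trial. The omission is certain; its size is conditional on an ICC that the documents do not give. For a test of change, the true error at nominal 5% lies between about 5.5% (ICC 0.01, intervention arm only) and 17% (ICC 0.10, both arms). At ICC 0.05 it is about 8% or 11% respectively. There is no inflation if clustering is purely constant over time and the test is arm-by-time. These figures rest on the target sample, the assumed unit split and two complete waves. The model should be corrected before any Aim 2 effectiveness result is relied on.

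**What to change.** State the tested contrast in the SAP, then include the randomised cluster (physician team-month; nursing unit) in one of two ways:

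1. A baseline-adjusted post-score model with a cluster random effect.
2. A repeated-measures model with a cluster random intercept plus a cluster-by-time random effect. The intercept alone does not correct an arm-by-time test.

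Cross cluster with clinician for attendings who serve in several months (allowed by protocol section 5.4), and use Kenward-Roger or Satterthwaite degrees of freedom because there are only six nursing units. Option 1, simulated over 3,000 runs with between-cluster degrees of freedom as a stand-in for Satterthwaite, held the error at 4.8%, 5.1% and 5.2% for change ICCs of 0.02, 0.05 and 0.10.

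The cost is a short SAP addition and no new data, since team and unit are already recorded. Intervals widen by about 11% at change ICC 0.02, 21% at 0.05 (0.1141/0.0966 = 1.18, times about 1.02 for the t reference) and about a third at 0.10. If there is no clustering, they widen by about 5%. Power falls accordingly: for an effect size of 0.3 without baseline adjustment, from 79.4% to 62.2% at ICC 0.05, since 0.3/√(1.50 × (1/167 + 1/177)) = 2.27 and Φ(2.27 − 1.96) = 62.2%. The FFMQ and WBI power statement should be restated on that basis.
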